11.5.2. Non-Serious Adverse Event Reporting Requirements

Non-serious adverse events will be reported to the Principal Investigator (or Protocol Chair) on the toxicity Case Report Forms.

11.6. Institutional Review Board (IRB) Notification by Investigator

The participating investigator will report all adverse events and serious adverse events to the Principal Investigator (or Protocol Chair) and to the IRB according to the local IRB’s policies and procedures in reporting adverse events.

In the event of a multi-center study, the Principal Investigator (or Protocol Chair) will report adverse events and serious adverse events from all participating sites to the DFCI IRB according to the IRB’s policies and procedures in reporting adverse events.

11.7. Hospital Risk Management Notification by Investigator

The participating investigator will report to the Principal Investigator (or Protocol Chair) and to local Risk Management any subject safety reports or sentinel events that require reporting according to institutional policy.

12. DATA AND SAFETY MONITORING

12.1. Data Reporting

12.1.1. Method

The QACT will collect, manage, and monitor data for this study.

Additionally, this study will be monitored by the Clinical Data Update System (CDUS) version 3.0. Cumulative CDUS data will be submitted quarterly to CTEP by electronic means. Reports are due January 31, April 30, July 31 and October 31. Instructions for submitting data using the CDUS can be found on the CTEP web site (<http://ctep.cancer.gov/>).

Note: All adverse events that have occurred on the study, including those reported through CTEP-AERS, must be reported via CTMS or CDUS.

12.1.2. Data Submission

The schedule for completion and submission of case report forms (paper or electronic) to the QACT is as follows:

Form	Submission Timeline
Eligibility Checklist	Complete prior to registration with QACT
On Study Form	Within 14 days of registration
Baseline Assessment Form	Within 14 days of registration
Treatment Form	Within 10 days of the last day of the cycle
Adverse Event Report Form	Within 10 days of the last day of the cycle
Response Assessment Form	Within 10 days of the completion of the cycle required for response evaluation
Off Treatment/Off Study Form	Within 14 days of completing treatment or being taken off study for any reason
Follow up/Survival Form	Within 14 days of the protocol defined follow up visit date or call

Participating sites are responsible for submitting CDUS data and/or data forms quarterly by January 15, April 15, July 15, and October 15 to allow time for Coordinating Center compilation,

Principal Investigator review, and timely submission to CTEP (see Section 12.1.1.). For trials monitored by CTMS, the monthly data submission to CTEP from Theradex should be copied to the Coordinating Center.

The DF/HCC sites participating in this study are responsible for compiling and submitting CDUS data to CTEP for all participants and for providing the data to the Principal Investigator for review. Data for non-DF/HCC institutions will be entered in CDUS by the lead institution.

12.2. Safety Meetings

The DF/HCC Data and Safety Monitoring Board (DSMB) will review and monitor toxicity and accrual data from this trial. The committee is composed of clinical specialists with experience in oncology and who have no direct relationship with the study. Information that raises any questions about participant safety will be addressed with the Principal Investigator and study team.

The DSMB will meet every 6 months and/or more often if required to review toxicity and accrual data. Information to be provided to the committee may include: up-to-date participant accrual; current dose level information; DLT information; all grade 2 or higher unexpected adverse events that have been reported; summary of all deaths occurring within 30 days for Phase I or II protocols; for gene transfer protocols, summary of all deaths while being treated and during active follow-up; any response information; audit results, and a summary provided by the study team. Other information (e.g. scans, laboratory values) will be provided upon request.

12.3. Monitoring

Involvement in this study as a participating investigator implies acceptance of potential audits or inspections, including source data verification, by representatives designated by the Principal Investigator (or Protocol Chair) or DF/HCC. The purpose of these audits or inspections is to examine study-related activities and documents to determine whether these activities were conducted and data were recorded, analyzed, and accurately reported in accordance with the protocol, institutional policy, Good Clinical Practice (GCP), and any applicable regulatory requirements.

All data will be monitored for timeliness of submission, completeness, and adherence to protocol requirements. Monitoring will begin at the time of participant registration and will continue during protocol performance and completion.

13. REGULATORY CONSIDERATIONS

13.1. Protocol Review and Amendments

This protocol, the proposed informed consent and all forms of participant information related to the study (e.g., advertisements used to recruit participants) and any other necessary documents must be submitted, reviewed and approved by a properly constituted IRB governing each study location.

Any changes made to the protocol must be submitted as amendments and must be approved by the IRB prior to implementation. Any changes in study conduct must be reported to the IRB. The Principal Investigator (or Protocol Chair) will disseminate protocol amendment information to all participating investigators.

All decisions of the IRB concerning the conduct of the study must be made in writing.

13.2. Informed Consent

All participants must be provided a consent form describing this study and providing sufficient information for participants to make an informed decision about their participation in this study. The formal consent of a participant, using the IRB approved consent form, must be obtained before the participant is involved in any study-related procedure. The consent form must be signed and dated by the participant or the participant's legally authorized representative, and by the person obtaining the consent. The participant must be given a copy of the signed and dated consent document. The original signed copy of the consent document must be retained in the medical record or research file.

13.3. Ethics and Good Clinical Practice (GCP)

This study is to be conducted according to the following considerations, which represent good and sound research practice:

- ICH Consolidated Good Clinical Practice: Guidelines (E6)
www.fda.gov/cder/guidance/iche6.htm
- US Code of Federal Regulations (CFR) governing clinical study conduct and ethical principles that have their origin in the Declaration of Helsinki
 - Title 21 Part 11 – Electronic Records; Electronic Signatures
www.access.gpo.gov/nara/cfr/waisidx_02/21cfr11_02.html
 - Title 21 Part 50 – Protection of Human Subjects
www.access.gpo.gov/nara/cfr/waisidx_02/21cfr50_02.html
 - Title 21 Part 54 – Financial Disclosure by Clinical Investigators
www.access.gpo.gov/nara/cfr/waisidx_02/21cfr54_02.html

- Title 21 Part 56 – Institutional Review Boards
www.access.gpo.gov/nara/cfr/waisidx_02/21cfr56_02.html
- Title 21 Part 312 – Investigational New Drug Application
www.access.gpo.gov/nara/cfr/waisidx_02/21cfr312_02.html
- State laws
- Institutional research policies and procedures www.dfhcc.harvard.edu/clinical-research-support/clinical-research-operations-cro/policies-and-procedures

It is understood that deviations from the protocol should be avoided, except when necessary to eliminate an immediate hazard to a research participant. In such case, the deviation must be reported to the IRB according to the local reporting policy.

13.4. Study Documentation

The investigator must prepare and maintain adequate and accurate case histories designed to record all observations and other data pertinent to the study for each research participant. This information enables the study to be fully documented and the study data to be subsequently verified.

Original source documents supporting entries in the case report forms include but are not limited to hospital records, clinical charts, laboratory and pharmacy records, recorded data from automated instruments, microfiches, photographic negatives, microfilm or magnetic media, and/or x-rays.

13.5. Records Retention

All study-related documents must be retained for the maximum period required by applicable federal regulations and guidelines or institutional policies.

13.6. Cooperative Research and Development Agreement (CRADA)/Clinical Trials Agreement (CTA)

CRADA INFORMATION

The agent(s) supplied by CTEP, DCTD, NCI used in this protocol is/are provided to the NCI under a Collaborative Agreement (CRADA, CTA, CSA) between the Pharmaceutical Company(ies) (hereinafter referred to as "Collaborator(s)") and the NCI Division of Cancer Treatment and Diagnosis. Therefore, the following obligations/guidelines, in addition to the provisions in the "Intellectual Property Option to Collaborator" (http://ctep.cancer.gov/industryCollaborations2/default.htm#guidelines_for_collaborations) contained within the terms of award, apply to the use of the Agent(s) in this study:

1. Agent(s) may not be used for any purpose outside the scope of this protocol, nor can Agent(s) be transferred or licensed to any party not participating in the clinical study. Collaborator(s) data for Agent(s) are confidential and proprietary to Collaborator(s) and shall be maintained as such by the investigators. The protocol documents for studies utilizing investigational Agents contain confidential information and should not be shared or distributed without the permission of the NCI. If a copy of this protocol is requested by a patient or patient's family member participating on the study, the individual should sign a confidentiality agreement. A suitable model agreement can be downloaded from: <http://ctep.cancer.gov>.
2. For a clinical protocol where there is an investigational Agent used in combination with (an)other investigational Agent(s), each the subject of different collaborative agreements, the access to and use of data by each Collaborator shall be as follows (data pertaining to such combination use shall hereinafter be referred to as "Multi-Party Data"):
 - a. NCI will provide all Collaborators with prior written notice regarding the existence and nature of any agreements governing their collaboration with NIH, the design of the proposed combination protocol, and the existence of any obligations that would tend to restrict NCI's participation in the proposed combination protocol.
 - b. Each Collaborator shall agree to permit use of the Multi-Party Data from the clinical trial by any other Collaborator solely to the extent necessary to allow said other Collaborator to develop, obtain regulatory approval or commercialize its own investigational Agent.
 - c. Any Collaborator having the right to use the Multi-Party Data from these trials must agree in writing prior to the commencement of the trials that it will use the Multi-Party Data solely for development, regulatory approval, and commercialization of its own investigational Agent.
3. Clinical Trial Data and Results and Raw Data developed under a Collaborative Agreement will be made available exclusively to Collaborator(s), the NCI, and the FDA, as appropriate and unless additional disclosure is required by law or court order.. Additionally, all Clinical Data and Results and Raw Data will be collected, used and disclosed consistent with all applicable federal statutes and regulations for the protection of human subjects, including, if applicable, the *Standards for Privacy of Individually Identifiable Health Information* set forth in 45 C.F.R. Part 164.
4. When a Collaborator wishes to initiate a data request, the request should first be sent to the NCI, who will then notify the appropriate investigators (Group Chair for Cooperative Group studies, or PI for other studies) of Collaborator's wish to contact them.
5. Any data provided to Collaborator(s) for Phase 3 studies must be in accordance with the guidelines and policies of the responsible Data Monitoring Committee (DMC), if there is a DMC for this clinical trial.

6. Any manuscripts reporting the results of this clinical trial must be provided to CTEP by the Group office for Cooperative Group studies or by the principal investigator for non-Cooperative Group studies for immediate delivery to Collaborator(s) for advisory review and comment prior to submission for publication. Collaborator(s) will have 30 days from the date of receipt for review. Collaborator shall have the right to request that publication be delayed for up to an additional 30 days in order to ensure that Collaborator's confidential and proprietary data, in addition to Collaborator(s)'s intellectual property rights, are protected. Copies of abstracts must be provided to CTEP for forwarding to Collaborator(s) for courtesy review as soon as possible and preferably at least three (3) days prior to submission, but in any case, prior to presentation at the meeting or publication in the proceedings. Press releases and other media presentations must also be forwarded to CTEP prior to release. Copies of any manuscript, abstract and/or press release/ media presentation should be sent to:

E-mail: [contact]

The Regulatory Affairs Branch will then distribute them to Collaborator(s). No publication, manuscript or other form of public disclosure shall contain any of Collaborator's confidential/ proprietary information.

14. STATISTICAL CONSIDERATIONS

This is a Phase I/II trial to investigate the combination of cediranib and olaparib in recurrent high-grade papillary-serous or endometrioid ovarian, fallopian tube, or peritoneal cancer and in metastatic triple-negative breast cancer.

14.1. Study Design/Endpoints

14.1.1. Primary Objectives

1. **Phase 1 Component:** Determine the dose limiting toxicity (DLT) and maximum tolerated dose (MTD) of cediranib in combination with olaparib in the treatment of recurrent ovarian, fallopian tube, and peritoneal cancer or metastatic triple-negative breast cancer.
2. **Phase 2 Component:** Investigate the efficacy of cediranib in combination with olaparib (as determined by progression-free survival (PFS)) at the MTD / recommended phase 2 dose (RP2D) compared to that of olaparib alone in patients with recurrent platinum-sensitive grade 2 or 3 papillary-serous or endometrioid ovarian, fallopian tube, or peritoneal cancer.
3. **Phase 1-T (tablet) Component:** Determine the dose limiting toxicity (DLT) and maximum tolerated dose (MTD) of cediranib in combination with olaparib (tablet

formulation) in the treatment of recurrent ovarian, fallopian tube, and peritoneal cancer.

14.1.2. Secondary Objectives

1. **Phase 1 Component:** Assess the toxicities of the combination of cediranib and olaparib in the treatment of recurrent ovarian, fallopian tube, and peritoneal cancer or metastatic triple-negative breast cancer
2. **Phase 2 Component:** Investigate tumor response rate, clinical benefit rate (response or stable disease x 16 weeks, as determined by RECIST 1.1 criteria, and overall survival for patients with recurrent platinum-sensitive grade 2 or 3 papillary-serous or endometrioid ovarian, fallopian tube, or peritoneal cancer treated with cediranib and olaparib at the RP2D compared to cediranib alone.
3. **Phase 1-T (tablet) Component:** Assess the toxicities of the combination of cediranib and olaparib in the treatment of recurrent ovarian, fallopian tube, and peritoneal cancer.

14.1.3. Study Design

Phase 1 and Phase 1-T

The Phase 1 and Phase 1-T components of this trial will employ a 3+3 design, escalating on 0/3 or 1/6 DLT, and de-escalating if 2 DLTs are encountered. Please refer to Section 5.3 for more trial-specific escalation details.

Probabilities of dose escalation (based on a binomial distribution) are tabulated below for a series of assumed true toxicity rates:

True Toxicity Rate	0.1	0.2	0.3	0.4	0.5	0.6	0.65	0.7	0.8	0.9
Probability of Escalation	0.91	0.71	0.49	0.31	0.17	0.08	0.053	0.032	0.009	0.001

At least 6 patients will be treated at MTD, and no more than 1 patient should experience a DLT at the MTD level. Based on the exact binomial distribution, we would be unlikely to escalate the dose if the true toxicity was 65% or greater ($p = 0.053$).

When the MTD has been determined and confirmed in at least 6 patients, up to an additional 8 patients may be enrolled at the MTD dose to gain experience at the MTD dose level.

Phase 2

To assess the clinical efficacy of the combination of cediranib and olaparib, a randomized two-arm study will be conducted with cediranib and olaparib combined at the RP2D compared to olaparib alone. Patients will be randomized after stratification for prior receipt of anti-angiogenic therapy and BRCA status.

Phase 1-T pharmacokinetic (PK) Expansion

When the MTD has been determined and confirmed in at least 6 patients, two cohorts of 6 patients evaluable for PK purposes will be enrolled at the MTD in order to assess PK for the study drugs.

14.1.4. Primary Study Endpoints

Phase I: The primary study endpoint for the Phase I portion of this trial will be establishment of the maximum tolerated dose (MTD) and the dose-limiting toxicity (DLT). The MTD will then be considered the recommended Phase 2 dose (RP2D).

Phase II: The primary study endpoint for the Phase II portion of this trial will be progression-free survival.

Phase I-T: The primary study endpoint for the Phase I-T portion of this trial will be establishment of the maximum tolerated dose (MTD) and the dose-limiting toxicity (DLT) with cediranib and the tablet formulation of olaparib.

14.1.5. Secondary Study Endpoints

Phase I: Secondary endpoints will include assessing the toxicities of cediranib in combination with olaparib in patients with recurrent ovarian, fallopian tube, and peritoneal cancer or metastatic triple-negative breast cancer.

Phase II: Secondary endpoints will include assessing response rate (as defined by RECIST criteria) and clinical benefit rate (response + stable disease \geq 16 weeks); and assessing overall survival.

Phase I-T: Secondary endpoints will include assessing the toxicities of cediranib in combination with olaparib (tablet formulation) in patients with recurrent ovarian, fallopian tube, and peritoneal cancer.

14.2. Sample Size and Data Analysis

The planned sample size will vary depending upon the number of patients accrued in the Phase I and Phase I-T components of the study. The Phase II component will randomize 90 patients (i.e., 45 patients in each arm). The Phase 1 component will be accrued at the DF/HCC and University of Chicago sites, with an anticipated accrual rate of 2 to 3 patients per month. The

Phase 1-T component will be accrued at the DF/HCC and NCI sites, with an anticipated accrual of 2 to 3 patients per month. We will plan on a multi-center accrual for the Phase 2 component of the study, with accrual planned to complete over an 18 month period.

The expected PFS to a platinum-based regimen in this setting is approximately 6 months (Markman *et al.*, 1991). The PFS observed with cediranib alone in this patient population was 5.2 months (Matulonis *et al.*, 2009). In the Phase II study of olaparib in BRCA mutation carriers, the estimated PFS ranged from approximately 2.5 months to 5.5 months between the 100mg BID and 400mg BID cohorts (Audeh *et al.*, 2010). In BRCA wild-type patients, the estimated response rate was 23.9% (Gelmon *et al.*, 2010), which is comparable to the 20% response rate observed with single-agent cediranib (Matulonis *et al.*, 2008). Given this similar activity and the observed data in the Audeh *et al.* Phase II trial, we therefore project a PFS in a control arm of olaparib alone to be similar to that of platinum-based regimens at 6 months. An increase in progression-free survival to 10.5 months (from the projected 6 months) would be considered of clinical interest. In the Phase II portion of the study, for a power of 86% to reject H_0 : Median PFS in both arms = 6 months in favor of H_1 : Median PFS of the group with olaparib combination > 10.5 months with an alpha of 0.10, 71 events (i.e., disease progressions) out of a total of 82 evaluable patients will be required to detect a hazard ratio of 0.5716 (experimental over control). We will therefore perform the final PFS analysis when the 71st evaluable patient experiences cancer progression. It is anticipated that 10% of subjects will not be evaluable, and thus the total number of subjects with platinum-sensitive disease to be enrolled in the Phase II portion of the study is 90. Progression-free survival will be evaluated by Kaplan-Meier analysis and Log-Rank test for between group comparison, and median survival times reported. To minimize the likelihood of exposing study patients to an inactive regimen, an interim assessment of the hazard ratio for disease progression (experimental over control) will be performed when the 36th patient experiences cancer progression. If the estimated hazard ratio at that time is 1 or greater, accrual to the study will be halted for futility.

Response rates with olaparib in patients with recurrent ovarian cancer have been reported at approximately 20% (Gelmon *et al.*, 2010). Second-line platinum results in a response rate of ~30% in patients who have had a treatment-free interval between 6 and 24 months. With an enrollment of 41 patients in each arm, there will be an 80% power to detect a difference in tumor response and clinical benefit rates as small as 29.5% with an alpha of 0.05. H_0 : single-agent olaparib response rate = cediranib and olaparib response rate = 20%. H_1 : cediranib and olaparib > 49.5%. The response rates will be compared by an exact test and 95% confidence intervals will also be reported.

The secondary endpoint of overall survival will also be evaluated by Kaplan-Meier analysis and Log-Rank test for between-group comparison, and median survival time will be reported.

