4. REGISTRATION PROCEDURES

4.1. General Guidelines for DF/HCC and DF/PCC Institutions

Eligible patients will be entered on study centrally through the Quality Assurance Office for Clinical Trials (QACT) at the Dana-Farber Cancer Institute at the time of study enrollment. Completed QACT eligibility checklists and signed consent forms should be faxed to the QACT at [contact] prior to subjects starting protocol treatment. The checklist will be reviewed at that time and the subject registered by the QACT Protocol Registrars [contact]).

Following registration, patients should begin protocol treatment within 5 days. Other issues that would cause treatment delays should be discussed with the Principal Investigator. If a patient does not receive protocol therapy following registration, the patient's registration on the study may be canceled. The Study Coordinator should be notified of cancellations as soon as possible.

Except in very unusual circumstances, each participating institution will order DCTD-supplied agents directly from CTEP. Agents may be ordered by a participating site only after initial IRB approval for the site has been forwarded by the Coordinating Center to the CTEP PIO ([contact]) except for Group studies.

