4.2. Registration Process for DF/HCC and DF/PCC Institutions

The QACT registration staff is accessible on Monday through Friday, from 8:00 AM to 5:00 PM Eastern Standard Time. In emergency situations when a participant must begin treatment during off-hours or holidays, call the QACT registration line at [contact] and follow the instructions for registering participants after hours.

Randomization can only be done between normal QACT business hours, 8:00 AM to 5:00 PM Eastern Standard Time.

The registration procedures are as follows:

1. Obtain written informed consent from the participant prior to the performance of any study related procedures or assessments.
2. Complete the protocol-specific eligibility checklist using the eligibility assessment documented in the participant's medical/research record. **To be eligible for registration to the study, the participant must meet each inclusion and exclusion criteria listed on the eligibility checklist.**

Reminder: Confirm eligibility for ancillary studies at the same time as eligibility for the treatment study. Registration to both treatment and ancillary studies will not be completed if eligibility requirements are not met for all studies.

3. Fax the eligibility checklist(s) and all pages of the consent form(s) to the QACT at [contact].

Exception: DF/PCC Affiliate sites must fax the entire signed consent form including HIPAA Privacy Authorization and the eligibility checklist to the Network Affiliate Office. The Network Affiliate Office will register the participant with the QACT.

4. The QACT Registrar will (a) validate eligibility, (b) register the participant on the study, and (c) randomize the participant when applicable.
5. The QACT Registrar will send an email confirmation of the registration and/or randomization to the person initiating the registration immediately following the registration and/or randomization.

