10.1.1. Definitions

Evaluable for toxicity. All participants who receive at least one dose of study treatment will be evaluable for toxicity from the time of their first treatment with cediranib and olaparib.

Evaluable for objective response. Only those participants who have measurable disease present at baseline, have received at least one cycle of therapy, and have had their disease re-evaluated will be considered evaluable for response. These participants will have their response classified according to the definitions stated below. (Note: Participants who exhibit objective disease progression or die prior to the end of cycle 1 will also be considered evaluable.)

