10.4.5. Progression-Free Survival

Progression-Free Survival (PFS) is defined as the duration of time from start of treatment to time of objective disease progression.

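### The primary PFS test is sized and triggered on evaluable patients, a term not defined for PFS, and PFS starts at treatment, so a randomised patient who is never treated has no PFS time

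*Combined protocol and SAP*

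**What the plan says.** Section 14.2 sets the Phase II size: "The Phase II component will randomize 90 patients (i.e., 45 patients in each arm"). It then bases the PFS test on 71 progressions among 82 evaluable patients, with 86% power, alpha 0.10 and hazard ratio 0.5716. It explains the gap between 82 and 90: "It is anticipated that 10% of subjects will not be evaluable". The final analysis is tied to that smaller set: "We will therefore perform the final PFS analysis when the 71st evaluable patient experiences cancer progression". The futility look "will be performed when the 36th patient experiences cancer progression", without the word evaluable. The sentence naming the Kaplan-Meier analysis and log-rank test gives no analysis population.

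Section 10.4.5 says that PFS "is defined as the duration of time from start of treatment to time of objective disease progression". Section 4.2 shows that randomisation happens at registration, before any drug is taken; the registrar will "b) register the participant on the study, and (c) randomize the participant when applicable". Section 4.1 expects treatment to start within 5 days of registration and adds: "If a patient does not receive protocol therapy following registration, the patient's registration on the study may be canceled".

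The term evaluable has two definitions. Sections 10.1.1 and 14.3.1 define it for toxicity, from the first treatment. Section 10.1.1 also defines it for objective response, where it admits the following: "Only those participants who have measurable disease present at baseline, have received at least one cycle of therapy, and have had their disease re-evaluated", plus anyone who progresses or dies before the end of cycle 1. Section 14.3.2, on response, rests conclusions on all eligible participants and bars efficacy conclusions from subset analyses that leave out early stoppers. It allows patients who took no study drug to be left out of the main response-rate analysis.

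**The concern.** A randomised comparison is protected by keeping every randomised patient in the arm assigned. Here the primary endpoint has no stated analysis set. The only definitions of evaluable depend on what happens after randomisation, and the PFS clock starts at an event that some randomised patients may never reach. Two statisticians could follow this text and analyse different patients.

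The arms are two drugs against one, and no blinding is described, so the decision not to start can differ by arm. If the combination arm loses more patients of poor prognosis, the test favours the combination; if the control arm does, the test is conservative. If losses are balanced, or unrelated to prognosis, there is no material bias.

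**Working it through.** **1. The plan's own figure.** Inputs from Section 14.2: 71 events, hazard ratio 0.5716 (6/10.5 = 0.5714), alpha 0.10, 1:1 allocation. By Schoenfeld's formula:

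power = Φ(|ln HR| × √d / 2 − z) = Φ(0.5593 × 8.426 / 2 − 1.2816) = Φ(1.075) = 0.859.

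This reproduces the stated 86% with one-sided alpha, which the section does not specify; two-sided 0.10 would give 0.762. The event arithmetic is not in question.

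**2. How many patients the undefined term can affect.** 90 − 82 = 8, or 8/90 = 8.9% (9 at the stated 10%). The documents do not say how many of these would be untreated, how they would split by arm, or their prognosis. These are assumptions below.

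**3. Type I error if patients are excluded.** Log-rank simulation with no true effect: 45 per arm, exponential PFS with median 6 months, uniform accrual over 18 months, one-sided 0.10, cut at the 71st event in the analysed set. Eight patients per arm have 2 or 3 times the hazard and progress only after day 28; the excluded patients come from these. There were 20,000 runs per cell, so the Monte Carlo standard error is about √(0.10 × 0.90 / 20,000) = 0.002.

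| Excluded (combination:control) | Type I error, 2 to 3 times the hazard |
|---|---|
| 2:1, 2:0 or 3:1 | about 0.105 to 0.12 |
| 4:4 | 0.10 |
| 6:2 | 0.13 to 0.15 |
| 2:6 | 0.06 to 0.08 |
| 8:0 | 0.17 to 0.22 |

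The first row is the one that fits a few never-treated patients. The other rows need all 8 to be excluded. The 8:0 split has probability of about 0.03 even if the odds of exclusion are twice as high on the combination. Averaged over all splits of 8, the error is 0.10 with equal odds and 0.12 to 0.13 with doubled odds.

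**4. All 90 kept.** With complete follow-up the error returns to 0.10 (0.099 and 0.096 at 2 and 3 times the hazard). If the 8 are kept but censored by day 28, the 6:2 split gives 0.137 to 0.154, about the same as excluding them. If half of the 8 have their later progression captured, it gives about 0.12.

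**5. Power and timing after the change.** With 71 events, formula power stays 0.859 at the design hazard ratio. The proportion of patients with an event falls from 71/82 = 86.6% to 71/90 = 78.9%. With no loss to follow-up, the 71st event falls at about 28.4 months with 90 patients against 34.1 with 82. If some of the 45 combination patients progress at the control rate, simulated power is 0.83 with 2 such patients and 0.80 with 4, against 0.85 with none.

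**The case against.** The strongest reply has four parts.

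- **The text does not exclude anyone from the test.** The 82 and the 10% appear in the sizing and the trigger, and can be read as an enrolment allowance. This stands: a reader might infer that 8 randomised patients will be removed from the log-rank test, but the documents only imply it. The allowance does not, however, supply a PFS time for a patient who never starts.
- **Section 14.3.2 already protects the comparison.** A reader might infer that early stoppers will be dropped from PFS. The all-eligible rule and the bar on efficacy conclusions from subset analyses largely rule that out. But the section concerns response, says eligible rather than randomised, allows never-treated patients to be omitted, and does not fit easily with planning for 10% non-evaluable.
- **The larger error rates model the wrong group.** This also stands. The assumption of no progression before day 28 resembles early stopping, and treatment is expected within 5 days of registration. For never-treated patients the small counts are the fair illustration.
- **All-randomised analysis adds little for patients who are never scanned.** Correct. Section 9.2 times scans by weeks of treatment, Section 5.6 follows vital status after treatment, and the request in Section 10.1.4 to document later progression refers to patients who discontinue.

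The missing word in the interim trigger is weak evidence on its own: 36 is about half of 71 and may be shorthand for the same count.

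**Conclusion.** The gap is real and should be fixed. The primary PFS test has no defined analysis set, and as written a patient who is randomised but never treated has no PFS time. The risk concerns mainly the never-treated; early stoppers are a lesser matter.

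The likely size is modest: one-sided type I error of about 0.105 to 0.12 against 0.10, if a few never-treated patients are lost unevenly and have 2 to 3 times the hazard. Reaching 0.13 to 0.15 needs all 8 to be excluded with a 6:2 split. A reader might infer from the 8:0 figures that the error could double; that needs every exclusion in one arm, and nothing in the documents supports it. The direction is also open, since losses concentrated in the control arm make the test conservative. Confidence is high in the textual gap, not in any material bias. The plan's power calculation is sound if alpha is one-sided.

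**What to change.** - **Section 14.2:** state that PFS and OS are analysed in all randomised patients by assigned arm, and that both the 36 and the 71 events are counted in that set.
- **Section 10.4.5:** measure Phase II PFS from randomisation, and count progression documented after treatment stops, in line with the request in Section 10.1.4.
- **Section 4.1:** state that cancelling a registration does not remove a randomised patient from the analysis.
- **Any evaluable set:** define it and keep it as a labelled sensitivity analysis.
- **Reporting:** give, by arm, the number of randomised patients with no disease assessment after baseline.

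The cost is wording; neither the number of patients nor the number of events changes. The statistical price is the dilution shown above if untreated or early-stopping combination patients progress at the control rate. The change does not remove bias from patients never scanned after baseline, who are censored near randomisation. That is why the count by arm is needed.
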